10.2 Cytomorphologic Assessment

Cytomorphologic assessment will be performed as in the pilot study by [name]. She will provide both a traditional characterization (QNS, normal, apocrine metaplasia, epithelial hyperplasia, or hyperplasia with atypia) [Zalles et al 1995] and a semiquantitative cytology index score (modified Masood score) [Masood et al 1990] and a consensus panel (QNS, benign, intermediate/atypia, atypia/suspicious) description [The Uniform Approach to Breast Fine-Needle Aspiration Biopsy 1997]. The Masood semiquantitative index score will be the primary measure determining morphologic change as we have observed that interpretive variance (≥ 3 points) is less using this system [Fabian 2002].

10.3 Nuclear Morphometric Assessments

Nuclear Morphometric Assessments will be performed at the University of Arizona by [name] and associates. Briefly, the cytomorphology slide is imaged, individual nuclei are acquired and stored in libraries. Morphometric analysis of approximately 40 features is performed to generate a cumulative score that reflects deviation from normality.

10.4 RNA Extraction and qRT-PCR Assessments

RNA extraction will be performed after microdissection of the third slide using an Acturus Autopix and Macro LCM caps (Arcturus, Mountain View, California). RNA from microdissected epithelial cells and residual whole slide scraping is obtained using a commercial protocol (Paradise Reagent Solution, Arcturus) optimized for formalin-fixed specimens [Petroff 2006B]. Material is heated in an overnight incubation with proteinase K to lyse cells and dissociate nucleic acids prior to harvesting. RNA is isolated using column based chromatography and treated with DNase to eliminate any residual DNA. Purified RNA is amplified with a single round of T7 based linear amplification (Paradise Reagent System, Arcturus) and converted to cDNA and stored at -80°C until all specimens from a subject can be run in a single batch. Quality of RNA is checked by PCR (QC Metric, Arcturus). The quantity of RNA is expressed relative to the level of that for a housekeeping gene. The housekeeping gene differed by type of marker to be detected. Markers expected to be in relatively high abundance (e.g., ER, Cyclin D1) were tested against actin which is highly expressed. Markers expected to be expressed in relatively low levels (e.g., proliferation markers, pS2, aromatase) were tested against TATA box binding protein (TBP), a housekeeping gene that is expressed at low levels. PCR reactions were run on an Applied Biosystems Prism 7000 Sequence Detection System. PCR values obtained with crossing threshold (CT) values if fewer than 30 cycles were considered valid for analysis [Giulietti 2001; Feldman 2002; Gjerdrum 2004; Goldworthy 1999; Liss 2002; Al-Taher 2000; Liviak 2001; DeCremoux 2003].

The primary purpose of qRT-PCR assessments on extracted RNA is to a) confirm presence of the targets for letrozole (aromatase) and estradiol (ER); b) provide indirect evidence of reduction in breast tissue estradiol through assessment of the estrogen response genes pS2 (trefoil factor-1) and GREB-1 [Rae 2005].

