1.0 Objectives

Our primary hypothesis is that proliferation and expression of other estrogen response genes in hyperplastic breast tissue obtained by RPFNA from high risk women on chronic HRT will be favorably modulated by six months of letrozole relative to placebo without substantially increasing hot flashes or worsening overall quality of life.

To test our hypothesis, we have formulated the following objectives:

- 1.1 To determine whether Ki-67 in hyperplastic foci of breast epithelium obtained by random periareolar fine needle aspiration from postmenopausal high-risk women on HRT is reduced by six months of letrozole.
- 1.2 To determine if letrozole causes an increase in hot flashes, fatigue, pain, stiffness; a deterioration in overall quality of life; as well as deleterious changes in bone turnover markers, total cholesterol:HDL ratio, and C-reactive protein.
- 1.3 To determine if morphologic characteristics as assessed by nuclear morphometric measurements and semiquantitative Masood index score improve with six months of letrozole.
- 1.4 To determine if six months of letrozole in women on a stable dose of hormone replacement results in consistent down modulation of estrogen responsive genes, particularly pS2 and GREB-1.

At the conclusion of this proof of principle study, we will have established a firm clinical and biological basis for a large randomized study of letrozole versus placebo in high-risk postmenopausal women requiring hormone replacement for symptom control with development of breast cancer as an endpoint. If aromatase inhibitor treatment is found to reduce risk of breast cancer in women receiving hormone replacement, it would provide middle age women with tools to alleviate perimenopausal symptoms while minimizing breast cancer risk.

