3.0 Summary of Study Plan

This is a multi-institution double-blind placebo-controlled trial to whose main endpoint is to determine if 6 months of letrozole (2.5 mg daily) can reduce proliferation as assessed by Ki-67 in high risk postmenopausal women on systemic hormone replacement therapy who have RPFNA evidence of hyperplasia with atypia or borderline atypia, and a minimum Ki-67 in a hyperplastic foci of $\geq 1.5\%$. Secondary efficacy endpoints include assessment of change in morphology by nuclear morphometry and the semi-quantitative Masood score index and change in qRT-PCR assessed estrogen response genes (GREB-1, pS2). Mammographic density and bioavailable estradiol and testosterone will be assessed as well. No difference in change between letrozole versus placebo is expected for mammographic breast density, Masood Index score, or serum hormones, but significant reductions are expected in Ki-67, expression of estrogen response genes by qRT-PCR, and the proportion of cells deemed abnormal by nuclear morphometry. Other secondary endpoints include change in biomarkers associated with bone and cardiovascular health, toxicity measurements using the NCI CTCAE version 3.0, BCPT Symptom Check List (Mayo Clinic) hot flash score, general fatigue inventory the Fibromyalgia Impact Questionnaire from the Health Assessment Questionnaire, (which assessed joint stiffness and functional impact). These are validated questionnaires and it should take no more than 10-15 minutes to complete all three questionnaires. We predict there will be little difference in most parameters between placebo and letrozole at 6 months in these women continuing their HRT. Exceptions may be arthralgias, fatigue in a minority of women, particularly those with sub-optimal 25-OH vitamin D levels. We will be assessing baseline and six month 25-OH vitamin D levels to determine if women with an increase in bone turnover markers, fatigue and arthralgias are likely to have underlying vitamin D insufficiency which is unmasked by use of letrozole. Subsequent to the 6-month RPFNA for assessment of biomarkers, toxicity and quality of life assessments, all women may receive optional open-label letrozole for an additional 6 months, followed by a third RPFNA and biomarker assessment. The primary purpose of the subsequent 6 months open label letrozole is to facilitate recruitment, but also to assess biomarker and toxicity endpoint changes with longer treatment. A DEXA scan will be performed at completion of study to document any effects on bone health.

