10.1 Ki-67

Breast Cells from RPFNA are pooled in modified cytolyt and sent to KUMC by express mail within 72 hours of RPFNA and all will be processed to slides within 96 hours. Cells are processed to thin prep slides via standard manufacturer's specifications.

A minimum of three slides will be made by a liquid-based cytologic technique: at least one each for cytomorphology, Ki-67 and microdissected prior to RNA extraction. Total epithelial cells will be delineated with Mayer's hematoxylin counterstain and proliferating cells with a MIB-1 antibody for Ki-7. Only baseline slides containing > 500 epithelial cells are processed and stained for Ki-7. Antigen retrieval is performed with 10 nmol/L citrate buffer (pH 6) in a Biocare (Walnut Creek, CA) decloaking chamber for two minutes at 120 degrees C. Slides are then stained with a MIB-1 monoclonal antibody (M7240 Dako Cytomation, Carpinteria, CA) at a 1:20 dilution in a Dako Autostainer [Khan 2005]. Hyperplastic clusters are preferentially assessed and the number of cells with unequivocal nuclear staining out of 500 cells assessed and recorded. Manual counting will be employed and scoring assessed by two laboratory technicians. The scores will consist of number of cells assessed, and number of positive cells for Ki-67. A separate score for each technician and a consensus score will be recorded. The consensus score will be utilized for analysis of the primary endpoint. Representative cell clusters are archived with a digital imaging system.

In the event that fewer than 500 epithelial cells are present in the Ki-67 slide on the follow-up RPFNA, the cytology slide will be destained and used for Ki-67 staining. If there are still less than 500 evaluable cells present when all slide material is combined the post-treatment value for Ki-67 will be considered as the proportion of epithelial cells staining positive for Ki-67 relative to the total number of epithelial cells present. If no staining for Ki-67 is observed and there are less than 500 evaluable cells, the value will be imputed as the reciprocal of the total number of evaluable cells present. If there is no staining and greater than 500 cells, the value will be assumed to be zero. Subjects with less than 100 evaluable cells will be considered not evaluable for Ki-67.

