12.2 Statistical Analysis

All analyses will be intent-to-treat. All subjects randomized will be evaluable for safety and all subjects that have both a pre and post specimen are evaluable for efficacy. Primary analysis of efficacy will be performed on all evaluable subjects and secondary analysis will be done on those subjects who received at least 3 months of study medication. From our experience we have very little missing data, however, if the missing data rate is above 5%, we will use multiple imputation to impute these values to perform the primary and secondary analyses.

The primary outcome will be change in Ki-67 (percent of cells expressing Ki-67) from baseline to 6 months. The two-sample t-test will be used to compare the change in Ki-67 between the letrozole and placebo groups. Any difference in baseline values of Ki-67 between the two groups would

be due to chance, however, if there is a significant difference, then analysis of covariance adjusting for baseline values will be performed. Due to potential skewness in these variables we will assess whether or not the Central Limit Theorem may be assumed. Given the sample size the existence of an extremely high degree of skewness would require the use of the Wilcoxon Signed Rank test.

For the secondary endpoints, similar methods as above will be used to compare the treatment and control groups at two time points for all markers, i.e., serum hormones, mammographic breast density, and clinical laboratory tests. We will also correlate change in the primary biomarker Ki-67 with change in other markers (e.g., bioavailable estradiol, pS2, GREB-1) using Pearson's correlation coefficient. Again, if there exists a high degree of skewness in these variables, Spearman's correlation will be utilized.

Multiple regression analysis will also be used to investigate whether changes in Ki-67 are due to variables other than treatment effect (e.g., age, cytomorphology, Gail risk; as well as the predictive effect of other biomarkers on modulation of Ki-67). Best subsets and stepwise approaches will be employed while controlling for treatment group.

For comparison of moderate or worse toxicities we will consider grade 3 toxicity or premature trial discontinuation as the critical events. The prevalence of events in the letrozole vs. the placebo arm will be examined by Fisher's exact test.

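### If Section 10.4's CT-below-30 rule is applied to this trial, a pS2 value that falls past the cut-off at 6 months leaves no change value, which can pull the arm comparison for Objective 1.4 toward zero

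*Combined protocol and SAP*

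**What the plan says.** Objective 1.4 asks whether six months of letrozole "results in consistent down modulation of estrogen responsive genes, particularly pS2 and GREB-1". Section 3.0 says that "significant reductions are expected in Ki-67, expression of estrogen response genes by qRT-PCR". Section 10.4 describes these genes as indirect evidence that breast-tissue estradiol falls.

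The trial's only validity rule for the assay is in Section 10.4: "PCR values obtained with crossing threshold (CT) values if fewer than 30 cycles were considered valid for analysis". The sentence is in the past tense and repeats the pilot report in Section 2.8. On normalisation, Section 10.4 says "The quantity of RNA is expressed relative to the level of that for a housekeeping gene"; for low-abundance markers such as pS2 that gene is TBP. Nothing says what happens to a CT of 30 or more.

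Section 12.2 says similar methods will "compare the treatment and control groups at two time points for all markers, i.e., serum hormones, mammographic breast density, and clinical laboratory tests". That list omits qRT-PCR, and no scale is given for it. The two genes are named only for a correlation: "We will also correlate change in the primary biomarker Ki-67 with change in other markers (e.g., bioavailable estradiol, pS2, GREB-1". On missing data, Section 12.2 says "if the missing data rate is above 5%, we will use multiple imputation to impute these values".

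For Ki-67, Section 10.1 does deal with low results: "If there is no staining and greater than 500 cells, the value will be assumed to be zero". With fewer than 500 cells and no staining, the value is one over the number of cells. Only samples with fewer than 100 cells are not evaluable.

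**The concern.** A change value needs a usable result at both visits. The expected effect of letrozole is to raise the 6-month CT. A woman whose expression falls past the cut-off would then drop out of the comparison, while a woman whose expression is unchanged would stay in. The loss depends on the outcome, and it falls more heavily on letrozole if letrozole works. For Ki-67 the plan separates a low result from inadequate material; for CT it does not.

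At stake is the mechanistic evidence for Objective 1.4. A real fall in pS2 could look smaller than it is, or be missed.

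**Working it through.** **1. Pilot yield (Section 2.8).** Of 21 women with paired material, 14 had good-quality RNA. pS2 was at low levels, and 8/14 = 57% had CT below 30 at both visits (exact 95% CI 29% to 82%). All were on letrozole. The other six are not split by visit. GREB-1 was not in the pilot panel. The trial's only power figure is for Ki-67 (48 per arm, 0.67 SD; the t-test gives 90.1%, matching the stated 90%), and this point does not touch it.

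**2. Model (all inputs assumed, since no CT distribution is given).** Target CT = mean + woman effect + within-woman noise + RNA input at that visit + letrozole shift at 6 months. Outcome = change in (target CT minus housekeeping CT), so RNA input cancels. A pair is valid if target CT is below 30 at both visits. 200,000 women per arm.

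**3. One example.** Mean 28, woman SD 1.5, noise SD 1.0, no input variation, shift 1 cycle.

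- SD of one CT = √(1.5² + 1.0²) = 1.80. P(valid baseline) = P(Z < (30 − 28)/1.80) = P(Z < 1.11) = 0.87.
- Both visits valid (simulated): 0.80 on placebo, 0.68 on letrozole.
- Follow-up loss given a valid baseline: 1 − 0.80/0.87 = 8% on placebo, 1 − 0.68/0.87 = 22% on letrozole.
- Estimated shift: valid pairs 0.83 of the truth; regression imputation from baseline within arm 0.72; keeping every 6-month value in women with a valid baseline 1.00.
- With shift 0, loss is 8% in both arms and the difference is 0.

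**4. Range.** The mean was set so that 57%, 80% or 90% of letrozole pairs were valid.

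- Expression-dominated settings: woman SD 2 or 3, noise SD 1 or 1.5, input SD 0 or 1.5, shift 1 or 2 cycles, between-woman SD of the shift 0 or 1.
- Input-dominated settings: woman SD 0.5 to 1.5, noise SD 0.5 to 1, input SD 2 to 3, constant shift of 1 or 2 cycles.

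| Letrozole pairs valid | 57% | 80% | 90% |
|---|---|---|---|
| *Expression-dominated* | | | |
| Follow-up loss, letrozole | 20–34% | 10–17% | 5–9% |
| Follow-up loss, placebo | 6–16% | 2–7% | 1–3% |
| Valid-pair difference, % of true shift | 60–94% | 78–97% | 86–98% |
| Same, no variation in response | 76–94% | 85–97% | 92–98% |
| Regression imputation from detectable values | 50–89% | 71–94% | 81–97% |
| Censored regression | 94–101% | 97–101% | 99–101% |
| *Input-dominated* | | | |
| Valid-pair difference, % of true shift | 90–99% | 95–100% | 96–100% |

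Repeat runs moved these limits by up to about 3 points. In the limiting case where all CT variation is RNA input, loss is still unequal (29% against 13%) but the difference is unbiased.

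**5. Power and error rate.** These use expression-dominated settings, a 1-cycle shift and a baseline-adjusted model.

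- At 57% valid and 32 per arm (48 × 14/21), power is 22–54% without censored values and 34–68% with them.
- At 90% valid and 48 per arm, it is 58–92% and 63–94%.
- With no effect, rejection was 3.7–5.8% at a nominal 5% for all methods.

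**The case against.** The strongest reply is that the plan does not order these values to be discarded. The sentence sits in past-tense pilot text and says only which values counted as valid. That stands: use of the rule in this trial is inferred. But it is the only rule in the trial's own assay section, and without it the plan has none for low signals.

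Second, the direction of loss does not guarantee material bias. The pilot reports technical difficulty with RNA, and if CT varies mainly through RNA input, normalisation leaves the comparison nearly unbiased. This also stands. A reader might take 6% as the least attenuation at pilot yield, from the expression-dominated settings; the documents do not support any floor.

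Third, the pilot yield is a weak guide. It came from leftover cells, whereas this trial has a dedicated RNA slide and an extra-cell requirement at entry (Section 4.3). A reader might infer that 43% of pairs will be lost here; nothing shows that. The entry requirement does not, however, cover the 6-month sample.

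Fourth, the 5% clause might be thought to repair the loss. The plan does not say that CT of 30 or more counts as missing. If it does, imputation learns only from values that passed the cut-off. It did not remove the bias, and in the example it did worse than valid pairs.

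Finally, the cut-off rests on cited sources not available here, so whether a CT of 30 or more is quantitative cannot be judged. Censoring does not need it to be: it uses only the fact that the signal was at or below the limit.

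**Conclusion.** The concern holds in conditional form. If CT below 30 is applied as the validity rule and letrozole lowers expression, 6-month values are lost because of the outcome, more often on letrozole. The comparison implied by Objective 1.4 is then pulled toward zero, or left nearly unbiased if RNA input dominates CT variation.

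The size is unknown. Under the assumed distributions, attenuation is about 0 to 40% at the pilot's yield (at most about 24% if all women respond alike) and about 0 to 14% at 90% valid pairs.

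The support is for pS2. A reader might extend it equally to GREB-1, but the documents give no CT data for that gene, so there it is only a possibility. Nor should the point be read as a threat to the trial's main result. The primary Ki-67 analysis is untouched, there is no bias when letrozole has no effect, and the error lies in the conservative direction. Confidence is medium. The change is worth making because the endpoint is a stated objective and the remedy is cheap.

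**What to change.** In Section 10.4, state whether CT below 30 applies to this trial. For samples that pass RNA quality control and have a valid housekeeping CT, record a target CT of 30 or more. Keep it as left-censored: expression at or below that implied by CT 30 relative to that sample's housekeeping gene. Treat only quality-control or housekeeping failures as missing.

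In Section 12.2, state that pS2 and GREB-1 are compared between arms on the log (normalised CT) scale among women with a valid baseline, using a method that accepts censored values. A censored regression adjusted for baseline would do, as would a rank test that allows sample-specific limits. Do not impute CT of 30 or more from detectable values. Report counts of CT of 30 or more by gene, arm and visit. Settle this before unblinding.

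The cost is wording and no new assays, but the laboratory must record these CTs, and the documents do not say that it does. Some may still reflect low RNA input after quality control. A censored regression needs a distributional assumption; under skewed or heavy-tailed CT distributions its estimate stayed at 97–105% of the truth in four assumed scenarios.

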10.5 Blood Assessments

- 10.5.1 Complete Blood Count and Metabolic Chemistry Profile will be performed at the participating sites at on-study, intermediate, and off-study visits. Results will be used to confirm absence of serious liver or renal dysfunction or blood dyscrasia.

Blood for all biomarker assays will be collected at the participating institutions in gel clot tubes, with serum separated according to standard procedures, 1-2 ml of serum aliquoted into six plastic tubes. These tubes will be labeled with the date and a study subject specific number, and then frozen and stored at -80°C until shipment on dry ice to KUMC. Assays on baseline, 6-month, and 12-month samples will be performed together in the same run to avoid batch variation.

10.5.2 Bioavailable Estradiol and Bioavailable Testosterone

We have extensive experience with use of serum hormones as biomarkers in clinical chemoprevention trials [Fabian 2002, 2004]. Serum levels of estradiol will be measured by sensitive radioimmunoassay at Ligand Assay and Core Analysis Laboratory at the University of Virginia following diethyl ether extraction at KUMC. The lower limit of detection at the Ligand Lab is 1.5 pg/ml and the intra-assay variation is 4.3%. Extraction prior to RIA avoids contamination by estrone sulfate and is often necessary to obtain accurate values in postmenopausal women on HRT [Dowsett 2005B]. Testosterone after diethyl ether extraction is also measured by a sensitive RIA with a lower limit of detection of 5 ng/dl and the intra-assay variation is 5%. SHBG will be assayed by an immunometric assay using the Immulite analyzer (Diagnostic Products Corp), with a lower limit of detection 0.2 nmol/L and intra-assay variation of 2.4%.

Bioavailable estradiol or testosterone is calculated from the fraction that is unbound to SHBG [Stumpf 1981]. Tracer amounts of tritiated estradiol or testosterone are added to aliquots of serum, ammonium sulfate is added to precipitate the SHBG with bound steroid, the sample is centrifuged, and then activity in the supernatant and the precipitate are measured in parallel by liquid scintillation counting. The percent activity in the supernatant is calculated to yield the fraction of bioavailable (non-SHBG bound) hormone. Sensitive chemiluminescent assays are being developed by the core analysis lab at the University of Virginia and may be used instead of RIA for analysis of estradiol and testosterone [Dowsett 2005B].

We do not anticipate any significant difference in change in estradiol or testosterone between the letrozole and placebo groups.

